7.2 BASELINE CHARACTERISTICS

Demographics (age, sex, race, ethnicity), informed consent date, weight, height and BMI at screening will be listed and summarized using descriptive statistics (number of subjects, mean, standard deviation, minimum, median and maximum for quantitative variables and the proportion of subjects for qualitative variables) by treatment group and overall for the safety population. No formal statistical comparison between groups will be performed.

Concomitant medication/medical history data, including clinical events, will be listed for all safety subjects.

7.3 TREATMENT COMPLIANCE

Subject must take study drug at the study site. Failure of treatment compliance will lead to termination of study. The necessary measures will be employed to ensure treatment compliance. The study drug will be dispensed or administered according to applicable standard operating procedures (SOPs). Study drug administration will be listed and ordered by cohort, treatment, subject and visit/day.

8 ANALYSIS OF PHARMACOKINETICS

The PK population will be used for all PK analysis and listings.

8.1 MEASUREMENTS

A 4 ml of blood sample were collected at each planned time point for measurement of drug concentration in plasma. The time and date of collection of each sample was recorded in CRF.

8.2 COLLECTION SCHEDULE

For SAD part, blood samples will be collected for plasma levels of RP3128 on Day 1 (Pre-dose, 0.25, 0.5, 1.0, 2.0, 4.0, 6.0, 8.0, 12.0, 24.0 and 48 hr), Day 5, Day 8 and Day 15. For MAD part, blood samples will be collected for plasma levels of RP3128 on Day 1 (Pre-dose, 0.25, 0.5, 1.0, 2.0, 4.0, 6.0, 8.0, 12.0 and 24.0 hr), Day 3, Day 5, Day 7 (Pre-dose, 0.25, 0.5, 1.0, 2.0, 4.0, 6.0, 8.0, 12.0 and 24.0 hr), Day 9 (48 hr), Day 10 (72 hr), Day 11 (96 hr), Day 12 (120 hr), Day 13 (144 hr) and Day 15 (192 hr).

8.3 DERIVED DATA AND HANDLING OF MISSING OR BELOW LLOQ DATA

8.3.1 Derivation of PK Parameters

PK parameters for RP3128 will be derived with validated SAS programs for all RP3128 dose levels by non-compartmental analysis of the plasma concentration data using actual sampling times.

The following pharmacokinetic variables will be derived:

SAD:

- Maximum observed plasma concentration (C_{max})
- Time to maximum plasma concentration (T_{max})
- Terminal half-life ($t_{1/2}$)
- Area under the plasma concentration-time curve from time zero until the last measurable time point (AUC_{0-t})
- Area under the plasma concentration-time curve from time zero to infinity time (AUC_{0-inf})
- Elimination rate constant (K_{el})

MAD:

- Maximum observed plasma concentration in the dosing interval (C_{max}) (Day 1, Day 7)

- Lowest observed plasma concentration in the dosing interval (C_{\min}) (Day 7)
- Plasma concentration at the end of the dosing interval (C_{trough}) (Day 3, Day 5, Day 7)
- Average concentration during the dosing interval (C_{av}) (Day 7)
- Time to maximum plasma concentration (T_{max}) (Day 1, Day 7)
- Area under the plasma concentration-time curve from time zero until the last time point with measurable concentration (AUC_{0-24}) (Day 1, Day 7)
- Degree of fluctuation $[(C_{\text{max}}-C_{\min})/C_{\text{av}}]$ (Day 7)
- Swing $[(C_{\text{max}}-C_{\min})/C_{\min}]$ (Day 7)

The PK parameters will be estimated as follows:

- The C_{max} and the corresponding T_{max} , C_{\min} and C_{trough} will be read directly from the concentration-time plot (observed data, not predicted data by the program).
- AUCs will be calculated using the linear trapezoidal rule.
- The terminal elimination rate constant (K_{el}) will be determined by log linear regression obtained on at least the 3 last quantifiable concentrations and will not include C_{max} . The adjusted square of the correlation coefficient (R-square adjusted) for the goodness of fit of the regression line through the data points must be at least 0.80 for the K_{el} value to be considered reliable. If fewer than 3 quantifiable concentrations are available after C_{max} or if R-square is less than 0.80, the K_{el} will be left uncalculated.
- $t_{1/2}$ is calculated by the program as $\ln 2 / K_{\text{el}}$. If K_{el} is not calculable, then $t_{1/2}$ will also remain missing.
- The AUC from 0 to infinity is calculated by the program as:
 $AUC_{0-\text{inf}} = AUC_{0-t} + AUC_{t-\text{inf}}$ where t is the sampling time point of the last measurable concentration. $AUC_{t-\text{inf}}$ is calculated by the program as: C_t / K_{el} , where C_t is the observed concentration at time t and K_{el} is the elimination rate constant during the apparent terminal elimination phase. If K_{el} is not calculable, $AUC_{0-\text{inf}}$ will be set to missing.
- The AUC extrapolation to infinity ($AUC_{t-\text{inf}}$) must be $\leq 20\%$ of the total area for $AUC_{0-\text{inf}}$ to be considered reliable.

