1 GLOSSARY OF ABBREVIATIONS

Abbreviation	Description
ADaM	Analysis Data Model
AE	Adverse Event
ALP	Alkaline Phosphatase
ALT (SGOT)	Alanine Aminotransferase
ANC	Absolute Neutrophil Count
ANCOVA	Analysis of Covariance
AST (SGPT)	Aspartate Aminotransferase
AUC	Area Under the Curve
AUC _{0-t}	Area Under the Plasma-Concentration Time Curve from Zero Up to the Last Measurable time point
AUC _{0-inf}	Area Under the Curve from Zero extrapolated to infinite time
BUN	Blood Urea Nitrogen
bpm	Beats per minute
CFB	Change from Baseline
CK	Creatinine kinase
CM	Concomitant Medication
C _{av}	Average concentration during the dosing interval
C _{max}	Peak Drug Concentration
C _{min}	Lowest observed plasma concentration in the dosing interval
C _{trough}	Plasma concentration at the end of the dosing interval
CRAC	Calcium Release Activated Calcium Channel
CRF	Case Report Form
CSR	Clinical Study Report
CTCAE	Common Terminology Criteria for Adverse Events
ECG	Electrocardiogram
eCRF	Electronic Case Report Form
FSH	Follicular Stimulating Hormone
GGT	Gamma Glutamyl Transpeptidase
HCV	Hepatitis C Virus
HIV	Human Immune Deficiency Virus
Hr	Hour
HV	Healthy Volunteers

Abbreviation	Description
ICH	International Conference on Harmonization
IMP	Investigational Medicinal Product
LAR	Late Phase Asthmatic Response
LPS	Lipopolysaccharide
K_{el}	Apparent terminal elimination rate constant
MAD	Multiple ascending dose
MCH	Mean Corpuscular Hemoglobin
MCHC	Mean Corpuscular Hemoglobin Concentration
MCV	Mean Corpuscular Volume
MedDRA	Medical Dictionary for Regulatory Activities
mmHg	Millimeters of mercury
MMSE	Mini Mental State Examination
MTD	Maximum Tolerated Dose
PCP	Phencyclidine
PFT	Pulmonary Function Test
PI	Principal Investigator
PK	Pharmacokinetic
PR	P wave, R wave interval
PT	Preferred Term
QRS	Q wave, R wave, and S wave complex
QTcB	QT wave complex corrected for heart rate using Bazette's formula
SAD	Single ascending dose
SAE	Serious adverse event
SAP	Statistical Analysis Plan
SAS	Statistical Analysis System
SDTM	Study Data Tabulations Model
SOC	System Organ Class
SOP	Standard Operating Procedure
SRC	Safety Review Committee
$t_{1/2}$	Half life
TEAE	Treatment Emergent AE
T_{max}	Time of C_{max}
K_{el}	Terminal Rate Constant

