4.2 SECONDARY ENDPOINTS

The secondary endpoints include PK parameters and biomarker assessments

SAD-PK Endpoints:

- Maximum observed plasma concentration (C_{\max})
- Time to maximum observed plasma concentration (T_{\max})
- Area under the plasma concentration-time curve from time zero until the last time point with measurable concentration (AUC_{0-t})
- Area under the plasma concentration-time curve from time zero to infinity (AUC_{0-inf})
- Apparent termination elimination rate constant (K_{el})
- Apparent terminal elimination half-life ($t_{1/2}$)

MAD-PK Endpoints:

- Maximum observed plasma concentration in the dosing interval (C_{\max}) (Day 1, Day 7)
- Lowest observed plasma concentration in the dosing interval (C_{\min}) (Day 7)
- Plasma concentration at the end of the dosing interval (C_{trough}) (Day 3, Day 5, Day 7)
- Average concentration during the dosing interval (C_{av}) (Day 7)
- Time to maximum plasma concentration (T_{\max}) (Day 1, Day 7)
- Area under the plasma concentration-time curve from time zero until the last time point with measurable concentration (AUC_{0-24}) (Day 1, Day 7)
- Degree of fluctuation [$(C_{\max}-C_{\min})/C_{av}$] (Day 7)
- Swing [$(C_{\max}-C_{\min})/C_{\min}$] (Day 7)
- Terminal half-life ($t_{1/2}$) (Day 1, 7)

MAD-Biomarker Endpoints:

- Levels of various biomarkers (Th1, Th2 and Th17 cytokines) following LPS or CD3/CD28 stimulation

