¹Mean calculated based on number of subjects (N).

Programming Note: X will be assigned as 1, 2, 3.... as per each RP3128 dose level. Time point may vary depending on the actual number of sample collection.

<Dose Level> = RP3128 25 mg, 50 mg, 100 mg, 200 mg, 400 mg in SAD

**Table 14.2.1.1.1.X.M RP3128 Plasma Concentrations (ng/mL) by Time Point (MAD) – Day 1
Safety Population
<Dose Level>**

Cohort /Subject	Time Point									
	0h	0.25h	0.5h	1h	2h	4h	6h	8h	12h	24h
xxxx	xxx.x	xxx.x	xxx.x	xxx.x	xxx.x	xxx.x	xxx.x	xxx.x	xxx.x	xxx.x
.....	xxx.x	xxx.x	xxx.x	xxx.x	xxx.x	xxx.x	xxx.x	xxx.x	xxx.x	xxx.x
Statistics										
N	xx	xx	xx	xx	xx	xx	xx	xx	xx	xx
Mean ¹	xxx.x	xxx.x	xxx.x	xxx.x	xxx.x	xxx.x	xxx.x	xxx.x	xxx.x	xxx.x
SD	xxx.xx	xxx.xx	xxx.xx	xxx.xx	xxx.xx	xxx.xx	xxx.xx	xxx.xx	xxx.xx	xxx.xx
CV (%)	xx.x	xx.x	xx.x	xx.x	xx.x	xx.x	xx.x	xx.x	xx.x	xx.x
Minimum	xxx	xxx	xxx	Xxx	Xxx	xxx	xxx	xxx	xxx	xxx
Median	xxx.x	xxx.x	xxx.x	xxx.x	xxx.x	xxx.x	xxx.x	xxx.x	xxx.x	xxx.x
Maximum	xxx	xxx	xxx	Xxx	Xxx	xxx	xxx	xxx	xxx	xxx

N= Number of subject for which plasma sample was collected at each time point.

¹Mean calculated based on number of subjects (N).

Programming Note: X will be assigned as 1, 2, 3.... as per each RP3128 dose level. Time point may vary depending the actual data.

<Dose Level> = RP3128 25mg, 100mg, 400mg in MAD

Table 14.2.1.1.2.X.M RP3128 Plasma Concentrations (ng/mL) by Time Point (MAD) – Day 7
Safety Population
<Dose Level>

Cohort /Subject	Time Point															
	0h	0.25h	0.5h	1h	2h	4h	6h	8h	12h	24h	48h	72h	96h	120h	144h	192h
xxxx	xxx.x	xxx.x	xxx.x	xxx.x	xxx.x	xxx.x	xxx.x	xxx.x	xxx.x	xxx.x	xxx.x	xxx.x	xxx.x	xxx.x	xxx.x	xxx.x
.....	xxx.x	xxx.x	xxx.x	xxx.x	xxx.x	xxx.x	xxx.x	xxx.x	xxx.x	xxx.x	xxx.x	xxx.x	xxx.x	xxx.x	xxx.x	xxx.x
Statistics																
N	xx	xx	xx	xx	xx	xx	xx	xx	xx	xx	xx	xx	xx	xx	xx	xx
Mean ¹	xxx.x	xxx.x	xxx.x	xxx.x	xxx.x	xxx.x	xxx.x	xxx.x	xxx.x	xxx.x	xxx.x	xxx.x	xxx.x	xxx.x	xxx.x	xxx.x
SD	xxx.xx	xxx.xx	xxx.xx	xxx.xx	xxx.xx	xxx.xx	xxx.xx	xxx.xx	xxx.xx	xxx.xx	xxx.xx	xxx.xx	xxx.xx	xxx.xx	xxx.xx	xxx.xx
CV (%)	xx.x	xx.x	xx.x	xx.x	xx.x	xx.x	xx.x	xx.x	xx.x	xx.x	xx.x	xx.x	xx.x	xx.x	xx.x	xx.x
Minimum	xxx	xxx	xxx	Xxx	Xxx	xxx	xxx	xxx	xxx	xxx	xxx	xxx	xxx	xxx	xxx	xxx
Median	xxx.x	xxx.x	xxx.x	xxx.x	xxx.x	xxx.x	xxx.x	xxx.x	xxx.x	xxx.x	xxx.x	xxx.x	xxx.x	xxx.x	xxx.x	xxx.x
Maximum	xxx	xxx	xxx	Xxx	Xxx	xxx	xxx	xxx	xxx	xxx	xxx	xxx	xxx	xxx	xxx	xxx

N= Number of subject for which plasma sample was collected at each time point.

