Programming Note: <Dose Level> = RP3128 25mg, 100mg, and 400mg.

X will be assigned as 1, 2, and 3 as per each RP3128 dose level.

Table 14.2.1.2.3.X.M RP3128 – Summary of PK parameters (MAD) – Day 7

**PK Population
<Dose Level>**

Cohort/Subject	C _{max} (ng/mL)	C _{min} (ng/mL)	AUC ₀₋₂₄ (ng·h/mL)	C _{av} (ng/mL)	Degree of Fluctuation	Swing	T _{max} (h)	T _{1/2} (h)
xxxx	xxx	xxx	xxx	xxx	xxx	xxx	xxx	xxx
xxxx	xxx	xxx	xxx	xxx	xxx	xxx	xxx	xxx
Statistics								
N	xx	xx	xx	xx	xx	xx	xx	xx
Mean	xxx.x	xxx.x	xxx.x	xxx.x	xxx.x	xxx.x	xxx.x	xxx.x
SD	xxx.xx	xxx.xx	xxx.xx	xxx.xx	xxx.xx	xxx.xx	xxx.xx	xxx.xx
CV (%)	xx.x	xx.x	xx.x	xx.x	xx.x	xx.x	xx.x	xx.x
Minimum	xxx	xxx	x.x	xxx	xxx	x.x	x.x	x.x
Median	xxx.x	xxx.x	xx.x	xx.x	xx.x	xx.x	xx.x	xx.x
Maximum	xxx	xxx	x.x	x.x	x.x	x.x	x.x	x.x
Geo Mean ¹	xxx.x	xxx.x	xxx.x	xxx.x	NA	NA	NA	NA
Geometric CV%	xx.x	xx.x	xx.x	xx.x	NA	NA	NA	NA

N=Number of subjects with derivable PK parameter.

¹: Geo Mean: Geometric means are based on the arithmetic means of ln-transformed values

Programming Note: <Dose Level> = RP3128 25mg, 100mg, and 400mg

X will be assigned as 1, 2, and 3 as per each RP3128 dose level.

Table 14.2.2.X.1.M Summary of Cytokines <expression value>: Change from Baseline (MAD)

Visit and Time Point	Statistic	Safety Population	
		Placebo (N=xx)	RP3128 (N=xx)
Baseline (Day 1, Pre-dose)	n	Xx	Xx
	Mean ± SD	xx.x ± x.xx	xx.x ± x.xx
	Median	xx.x	xx.x
	Min, Max	xx , xx	xx , xx
Day 7 (Pre-dose)	n	xx	Xx
	Mean ± SD	xx.x ± x.xx	xx.x ± x.xx
	Median	xx.x	xx.x
	Min, Max	xx , xx	xx , xx
Change from Baseline ¹	n	xx	Xx
	Mean ± SD	xx.x ± x.xx	xx.x ± x.xx
	Median	xx.x	xx.x
	Min, Max	xx , xx	xx , xx
	Paired t-test	x.xx	x.xx
Day 7 (4 hr Post-dose)			
Change from Baseline ¹			
Change from Baseline ²			

Note: 1 Baseline set at Day 1 pre-dose;
2 baseline set at Day 7 pre-dose

Data source: Listings 16.2.6.1

Programming note: Replace <expression value> with Th1, Th2, and Th17 and X will be assigned as 1, 2, and 3 for expression Th1, Th2 and Th17 respectively

Table 14.2.2.X.2.M ANCOVA Results of Cytokine <expression value> Change from Baseline to Day 7 (Pre-dose/Post-dose)/ Difference between Pre-dose and Post-dose on Day 7 (MAD)

Safety Population

Item	Treatment	n	LSMeans	Std Err	Difference between RP3128 to Placebo				
					LSMeans	Std Err	95%-confidence Interval	P-value Treatment	P-value Baseline
CFB Day 7 (Pre-dose)	Overall	xxx						x.xxxx	x.xxxx
	Placebo	xxx	x.xxx	x.xxx					
	RP3128	xxx	x.xxx	x.xxx	x.xxx	x.xxx	x.xxx, x.xxx	x.xxxx	

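### The MAD AUC0-24 is defined in the words the SAP uses for AUC0-t, so on Day 7, with sampling to 192 h, definition and label describe different areas

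*SAP*

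**What the plan says.** The MAD lists in Section 4.2 (Secondary Endpoints) and Section 8.3.1 (Derivation of PK Parameters) both describe AUC0-24 as the area from time zero "until the last time point with measurable concentration (AUC_{0-24}) (Day 1, Day 7"). The SAD list in Section 4.2 describes another parameter in the same words: "until the last time point with measurable concentration (AUC_{0-t").

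The SAP is clear about what those words mean. The glossary explains AUC0-t as "Area Under the Plasma-Concentration Time Curve from Zero Up to the Last Measurable time point", and the AUC0-inf formula in Section 8.3.1 adds "where t is the sampling time point of the last measurable concentration". AUC0-24 has no glossary entry. The only calculation rule for areas in Section 8.3.1 is the linear trapezoidal rule, with no upper time limit.

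Section 8.2 ends the Day 1 profile at 24 h. After the Day 7 dose it continues with samples at 48, 72 and 96 h and then "Day 12 (120 hr), Day 13 (144 hr) and Day 15 (192 hr"). Appendix C, footnote 15, repeats this schedule. The shell of Table 14.2.1.1.2.X.M sets out the Day 7 concentrations from 0 h to 192 h as one profile, and the Day 7 parameter shell ("Table 14.2.1.2.3.X.M RP3128") has a column headed AUC0-24. Cav is described as "Average concentration during the dosing interval", without a formula.

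**The concern.** One written definition serves two differently named parameters, and for the MAD part it conflicts with the name. A SAP's written definitions are what programs are built and validated against. Here a programmer who follows the subscript and a validator who follows the sentence could produce different Day 7 values, and each could cite the SAP.

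The risk is realistic because the late samples are needed on Day 7 anyway. Section 4.2 and the Day 7 shell call for a terminal half-life, and Kel is fitted to at least the last three quantifiable concentrations. The Day 7 data set will therefore normally extend beyond 24 h.

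At stake is the description of multiple-dose exposure at steady state, a secondary objective. AUC0-24 is tabulated under the same heading for Day 1 and Day 7. If the words were programmed, the two columns would cover different time spans, and a reader comparing them would overstate accumulation. If Cav were then computed from that area, the error would carry into Cav and the degree of fluctuation.

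**Working it through.** **Label against words**

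| | Upper limit by the label | Upper limit by the words | Agreement |
|---|---|---|---|
| Day 1 | 24 h | last measurable sample, at most 24 h | yes, if the 24 h sample is taken and measurable |
| Day 7 | 24 h | last measurable sample, at most 192 h | no, whenever a sample after 24 h is measurable |

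The words could also stop the area short of 24 h if the 24 h sample is below LLOQ.

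**Size of the difference (illustration only)**

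The SAP states no figure that can be reproduced here. From the SAP come seven once-daily doses, the Day 7 sampling times (0, 0.25, 0.5, 1, 2, 4, 6, 8, 12, 24, 48, 72, 96, 120, 144, 192 h) and the linear trapezoidal rule. Assumed are a one-compartment oral model, absorption rate ka = 1/h, the half-life, and the LLOQ as a fraction of Day 1 Cmax. With k = ln 2 / half-life, and the dose scale cancelling in ratios:

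C(t) = sum over i = 0 to 6 of ka/(ka − k) × [exp(−k(t + 24i)) − exp(−ka(t + 24i))]

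The ratio is the Day 7 area to the last value at or above LLOQ, divided by the Day 7 area over 0-24 h. A value below LLOQ within 0-24 h is set to LLOQ in the denominator, following Section 8.3.2.

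*Worked case, half-life 24 h, LLOQ 1%.*
- Day 1 Cmax is 0.8985, so LLOQ is 0.0090. The modelled value is 0.0319 at 144 h and 0.0080 at 192 h, so the last measurable time is 144 h.
- The 0-24 h area is 34.43.
- The later trapezoids add 18.39 + 9.20 + 4.60 + 2.30 + 1.15 = 35.64, or 35.63 before rounding.
- Ratio: (34.43 + 35.63)/34.43 = 2.03.

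*Ratios over the assumed range, with the last measurable time in brackets:*

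| Half-life | All samples measurable | LLOQ 1% | LLOQ 5% |
|---|---|---|---|
| 4 h | 1.04 | 1.00 (24 h) | 0.815 (12 h) |
| 6 h | 1.11 | 1.00 (24 h) | 1.00 (24 h) |
| 12 h | 1.40 | 1.38 (72 h) | 1.30 (48 h) |
| 18 h | 1.73 | 1.71 (120 h) | 1.61 (72 h) |
| 24 h | 2.06 | 2.03 (144 h) | 2.00 (120 h) |
| 36 h | 2.70 | 2.70 (192 h) | 2.70 (192 h) |
| 48 h | 3.26 | 3.26 (192 h) | 3.26 (192 h) |
| 72 h | 4.14 | 4.14 (192 h) | 4.14 (192 h) |

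*The value below 1.* At 4 h and LLOQ 5%, LLOQ is 0.0346 and the 24 h value of 0.0192 falls below it. The area by the words stops at 12 h with 4.983. The 0-24 h area is 4.983 + 12 × (0.1536 + 0.0346)/2 = 6.112, and 4.983/6.112 = 0.815.

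Section 8.3.2 can be read as setting the Day 7 pre-dose sample to zero. Doing so moves no ratio by more than 0.02.

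**Effect on apparent accumulation (LLOQ 1%)**

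At a 24 h half-life the Day 7/Day 1 ratio is 2.05 by the label and 4.17 by the words. At 48 h it is 3.23 by the label and 10.54 by the words.

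**The case against.** The strongest reply is that the SAP makes its intent plain. The subscript 0-24 is used throughout for the MAD part, and AUC0-t is listed only for SAD. Cmax, Cmin, Ctrough and Cav are tied to the dosing interval, which is 24 h. Section 8.2 lists the 48 to 192 h samples under Day 9 to Day 15, not Day 7. The 0-192 h shell is only a concentration table, and the late samples can serve the Day 7 half-life. Anyone filling a column headed AUC0-24 would have to ignore the heading to integrate to 192 h.

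This stands as evidence of intent, and 0-24 h is the likely meaning. It does not repair the definition: apart from the subscript, no text gives the area a 24 h limit, and the sentence says something else.

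Three further points stand:
- The ratios rest wholly on assumed values and are not bounds. A 96 h half-life gives 4.77 and 120 h gives 5.23, while at 4 to 6 h with LLOQ 1% there is no difference.
- The 0.815 depends on counting the below-LLOQ 24 h value in one area only. Carrying it in both gives 1.00, so stopping short of 24 h is a possible reading, not a certain one.
- Areas use actual sampling times and uncollected samples are not imputed, so a 24 h limit works best with a rule for a missing or off-time 24 h sample.

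**Conclusion.** The definition of AUC0-24 in Sections 4.2 and 8.3.1 is wrong as written: it is the SAP's own definition of AUC0-t. The conflict bites mainly on Day 7. This is a definition error with a programming risk, not evidence that a wrong value was or will be reported.

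Its size depends on pharmacokinetics that the SAP does not give. Under the one-compartment assumptions above it ranges from nothing at a short half-life to about a doubling of the Day 7 area at 24 h and about a fourfold area at 72 h. PK is summarised descriptively, so no test and no primary endpoint is affected. Because a secondary endpoint's definition contradicts its name and the correction is simple, it should be fixed.

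**What to change.** - In the MAD lists of Sections 4.2 and 8.3.1, define AUC0-24 as *the area under the plasma concentration-time curve from time zero to 24 h after that day's dose*.
- Add one line to Section 8.3.1: Cav (Day 7) = AUC0-24/24. This agrees with its existing description over the dosing interval.
- If a Day 7 area to the last measurable concentration is also wanted, name it AUC0-t and report it separately.
- Optionally, add a sentence on how AUC0-24 is obtained when the 24 h sample is missing or taken off its nominal time.

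The cost is one phrase in two sections and one line for Cav, plus the optional sentence. No new data or samples are needed.

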3.5 DETERMINATION OF SAMPLE SIZE

The sample size has been selected without performing a power calculation to provide descriptive information on the safety, tolerability, and PK following administration of RP3128. This trial enrolled up to 56 HV (32 in SAD and 24 in MAD). Number of subjects enrolled in this study is in line with standard phase I studies and is considered sufficient to provide descriptive information on the pharmacokinetics, safety and tolerability of RP3128 while minimizing exposure to humans. The actual number of dose cohorts will depend upon the emerging safety data.

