3.7 ADMINISTRATION OF STUDY MEDICATION

Depending on the cohort, specific dose/doses of RP3128/placebo was dispensed by pharmacy staff during the study. RP3128/placebo capsules was administered orally in the morning with approximately 240 mL (8 fluid ounces) of water at room temperature by the subject. For SAD part, the doses in 5 planned cohorts were 25 mg, 50 mg, 100 mg, 200 mg and 400 mg. For MAD part, the doses in 3 planned cohorts were determined to be 25mg, 100mg, and 400mg considering the safety and PK profile of RP3128 in SAD.

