8.3.2 Handling of Missing Plasma Concentration Data or below LOQ

Plasma concentrations can only be missing if the sample was not collected. These missing concentrations will be considered as non-informative missing and will not be imputed.

However, if a plasma sample was collected, but the resulting assay failed to detect a quantifiable concentration, these will be imputed in the following way:

- Concentration values below the assay's lower limit of quantification (<lower limit of quantification (LLOQ) or below the limit of quantification (BLQ)) in pre-dose samples and

in samples taken before the time of the first quantifiable concentration will be treated as zero.

- All sample collected prior to dosing will be treated as zero.
- Post-dose BLQ values after the first quantifiable time point that are flanked and followed by quantifiable concentrations will be set to LLOQ.
- Post-dose BLQ values after the first quantifiable time point that are not followed by quantifiable concentrations will be set to LLOQ.
- For PK profiles with no values reported above the LLOQ, these BLQ values will be set to LLOQ.

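### SAD AUC: the linear trapezoidal rule across sampling gaps of 48, 72 and 168 h overstates AUC0-t by roughly 0 to 8%, which a log-down rule would largely remove

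*SAP*

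**What the plan says.** SAP section 8.3.1 sets one rule for every AUC: "AUCs will be calculated using the linear trapezoidal rule". The derivation is done "by non-compartmental analysis of the plasma concentration data using actual sampling times". Kel comes from log-linear regression on at least the last three quantifiable concentrations. AUC0-inf is AUC0-t plus Ct/Kel, "where t is the sampling time point of the last measurable concentration", and the extrapolated part must be no more than 20% of the total for AUC0-inf to count as reliable.

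Section 8.2 gives the SAD sampling times as pre-dose and then "0.25, 0.5, 1.0, 2.0, 4.0, 6.0, 8.0, 12.0, 24.0 and 48 hr), Day 5, Day 8 and Day 15". The shell for Table 14.2.1.1.X.S labels the last three columns 96, 168 and 336 h. Section 3.7 gives the dose range: "For SAD part, the doses in 5 planned cohorts were 25 mg, 50 mg, 100 mg, 200 mg and 400 mg". Section 8.4 summarises AUC by treatment with descriptive statistics. The SAP plans no dose-proportionality model or test.

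**The concern.** While a concentration declines exponentially, the straight line between two samples lies above the curve, so each interval in the decline adds a positive error that grows with its width relative to the half-life. Using actual sampling times does not shorten the gaps. AUC0-t stops at the last measurable concentration, so the number of wide gaps it includes depends on how long a subject stays quantifiable, and that depends on dose. AUC0-inf is built on AUC0-t and inherits the error.

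There is also a mismatch within section 8.3.1. The area beyond the last sample is computed as exponential, while the area between the last few samples of the same phase is computed with straight lines.

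SAD pharmacokinetics are a secondary objective (section 3.2), and AUC0-t and AUC0-inf are named endpoints (section 4.2). At stake is a small error, mostly in one direction, in the reported exposure. It may differ somewhat between dose levels, and more subjects would not average it out.

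**Working it through.** The SAP gives no AUC bias figure to reproduce. The check compares the linear trapezoid on the SAD grid with the exact integral.

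**Inputs from the SAP**
- Sampling times: 0, 0.25, 0.5, 1, 2, 4, 6, 8, 12, 24, 48 h, then Days 5, 8 and 15.
- (Day - 1) × 24 h gives 96, 168 and 336 h, matching the table shell. The gaps after 48 h are 48, 72 and 168 h.
- Doses of 25 to 400 mg, a 16-fold range.

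**Assumptions (not in the SAP)**
- One-compartment oral curve, ka = 1/h, half-life 12 to 200 h.
- LLOQ varied as a fraction of the 25 mg Cmax.
- Trailing values below LLOQ, which section 8.3.2 sets to LLOQ, are taken as not measurable and so do not extend AUC0-t.

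**Step 1: error within one gap.** For exponential decline, linear area / true area = x·coth(x), with x = ln 2 × gap / (2 × half-life). For a 48 h half-life and the 168 h gap, x = 0.693 × 168 / 96 = 1.213 and x·coth(x) = 1.448, an excess of 44.8%.

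| Half-life | 48 h gap | 72 h gap | 168 h gap |
|---|---|---|---|
| 24 h | +15.5% | +33.7% | +146% |
| 48 h | +4.0% | +8.9% | +44.8% |
| 96 h | +1.0% | +2.2% | +12.0% |

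**Step 2: why the total error is much smaller.** The wide gaps hold little of the area. At a 48 h half-life, the intervals 48-96, 96-168 and 168-336 h hold 25.37%, 16.40% and 8.18% of total AUC. Multiplying by the excesses (3.97%, 8.86% and 44.8% before rounding) gives 1.01 + 1.45 + 3.66 = 6.12 percentage points. The shorter intervals bring the AUC0-inf bias to +6.3%.

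**Step 3: bias of the whole AUC0-t, by last quantifiable sample**

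| Half-life | 48 h | 96 h | 168 h | 336 h |
|---|---|---|---|---|
| 12 h | +4.1% | +7.4% | +7.8% | +7.9% |
| 24 h | +1.4% | +4.3% | +6.0% | +7.1% |
| 48 h | +0.3% | +1.5% | +2.9% | +6.3% |
| 72 h | +0.1% | +0.7% | +1.5% | +4.8% |
| 96 h | 0.0% | +0.4% | +0.9% | +3.5% |
| 200 h | -0.1% | 0.0% | +0.2% | +1.1% |

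Linear-up/log-down on the same samples gives -0.4% to 0.0% in all these cells. Varying ka from 0.3 to 2/h and half-life from 8 to 200 h raises the maximum for the linear rule to about 9% and widens the log-down range to -1.4% to 0.0%.

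**Step 4: difference between 25 and 400 mg.** Under identical, dose-proportional PK, a 16-fold dose adds log2(16) = 4 half-lives of quantifiable time.
- Half-life 24 h (4 × 24 = 96 h): if the last quantifiable 25 mg sample is at 48 h, concentrations cross LLOQ between 48 and 96 h. At 400 mg they cross between 144 and 192 h, so the last sample is at 96 or 168 h. The difference is 4.3 - 1.4 = 2.9 or 6.0 - 1.4 = 4.6 points.
- Half-life 48 h, LLOQ at 10% of the 25 mg Cmax: 25 mg reaches 96 h (+1.5%) and 400 mg reaches 336 h (+6.3%), a difference of 4.8 points.
- Half-life 72 h, LLOQ at 2% of the 25 mg Cmax: both doses reach 336 h and the difference is 0.

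**Step 5: two-phase decline.** For an assumed curve with half-lives of 6 and 96 h, the linear rule gives +4.4, +4.1, +3.8 and +5.0% at 48, 96, 168 and 336 h, so relative bias does not rise steadily. Log-down gives +2.0, +1.9, +1.6 and +1.4%.

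**The case against.** The linear trapezoidal rule is a recognised non-compartmental method and the SAP specifies it clearly. The effect is a few percent on descriptive output. With 3 active subjects at 25 mg and 6 at 400 mg (section 3.6), and an assumed between-subject CV of 30%, the log-scale SD is √ln(1.09) = 0.294. The 95% interval for a ratio of geometric means is then exp(±2.365 × 0.294 × √(1/3 + 1/6)), or 0.61 to 1.63 times the estimate. A 5% artefact would not be visible there. All of this stands and limits the weight of the point.

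A reader might also draw three stronger conclusions that the SAP does not support.

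- **About 6 points between doses.** Subtracting within the 24 h row of the table, 7.1 - 1.4 = 5.7, pairs a low dose lost after 48 h with a high dose quantifiable at 336 h. Under dose-proportional PK that pair cannot occur. For 400 mg to reach 336 h, 25 mg must stay quantifiable to 336 - 96 = 240 h. Its last sample is then at 168 h, and the difference is 7.1 - 6.0 = 1.1 points.
- **A distorted AUC0-inf comparison.** The low-dose cases above with the larger contrasts carry about 25% extrapolation (25.5% for half-life 24 h and last sample 48 h; 25.1% for 48 h and 96 h). They fail the SAP's own 20% limit.
- **Log-down makes AUC0-t comparable across doses.** It does not. At a 24 h half-life, AUC0-t covers 74% of total AUC when it stops at 48 h and 99% at 168 h. That 25-point truncation difference is far larger than the 4.6 points from the rule, and it remains after the change.

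The objection does not remove the point itself: the gaps are as stated, the direction of error across them follows from the shape of the decline, and the same samples allow a less biased calculation.

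**Conclusion.** The point holds as a small, inexpensive improvement to SAD AUC. It is not an error that distorts a planned comparison. Under a one-compartment decline with assumed half-life 12 to 200 h and ka 1/h, the linear rule overstates AUC0-t by about 0 to 8%, usually more when later samples are quantifiable. The artefactual difference between 25 and 400 mg is 0 to about 5 points. The bias is close to 1% or less at a half-life of 200 h, and it need not increase steadily when the decline has two phases. The size rests on half-life, absorption rate and LLOQ, none of which the SAP gives. MAD AUC0-24, with gaps of at most 12 h, is barely affected.

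**What to change.** In section 8.3.1, state that SAD AUC0-t and AUC0-inf use the linear trapezoidal rule while concentrations rise or are equal, and the logarithmic trapezoidal rule while they fall (linear-up/log-down). Naming equal concentrations matters because the logarithmic formula is undefined there. Zeros do not arise in the falling phase: section 8.3.2 sets values below LLOQ after the first quantifiable sample to LLOQ (for the trailing ones, "Post-dose BLQ values after the first quantifiable time point that are not followed by quantifiable concentrations will be set to LLOQ"). Applying the rule to MAD AUC0-24 is optional, for consistency.

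The cost is one sentence, a small change to the SAS derivation and slightly lower AUCs. Truncation of AUC0-t would still need to be kept in mind when doses are compared.
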